7.2.6 Treatment Compliance

Subjects will complete a subject diary recording daily applications of the medications to the treatment area on the face. Each medication is to be applied twice daily.

7.2.7 Concomitant Medications and Treatments

A log of medications taken and procedures performed during the study will be recorded for each subject.

7.2.8 Efficacy Analyses

Efficacy variables will be analyzed at the time points shown in the visit schedule.

7.2.8.1 Primary Efficacy Analyses

This study is concerned with the efficacy of topical AFX 5931 in the treatment of mild to moderate hand dermatitis. Changes in clinical scores recorded via the Hand Eczema Severity Index and Investigator's Global Assessment will be the primary modes of efficacy evaluation.

7.2.8.2 Safety Analyses

Safety analyses will be performed on the safety population. The Local Skin Reaction Assessment and the Subject's Local Dermal Tolerability Assessment will be the primary modes of tolerability evaluation. Monitoring the record of AEs and changes in concomitant medication throughout the course of the study will be the primary mode of safety evaluation. In addition, the frequency and percentage of subjects with adverse events will be summarized by coded body system and preferred term for each treatment group using the Medical Dictionary for Regulatory Activities (MedDRA). At each level of summarization (global, body system, and preferred term), a patient will be counted once if he/she has reported one or more AEs at that level. Tabular summaries will be presented for all adverse events, by severity, by

relationship to treatment, and for serious adverse events. No statistical testing will be performed. Changes in concomitant medications/procedures will also be monitored.

7.3 Source Documents

The full dataset will be collected for all subjects enrolled. All required data for this study will be collected on paper source document worksheets. The collected data will be entered into a validated database. Database lock will occur once quality assurance procedures have been completed.

Source data is all information, original records of clinical findings, observations, or other activities in a clinical trial necessary for the reconstruction and evaluation of the trial. Source data are contained in source documents. Examples of source documents include hospital records, office charts, memoranda, evaluation checklists, photographs, and subject files.

All procedures for the handling and analysis of data will be conducted using good computing practices meeting USFDA guidelines for the handling and analysis of data for clinical trials.

7.4 Data Capture

Data will be captured on CRFs. CRFs are the primary data collection instrument for the study. All data on the CRF will be recorded, and all missing data must be explained. All data collected for the study and entered into the CRF must be traceable to a source document.

The Investigator will review, approve, and sign off on the CRFs. The Investigator's signature will serve as a testament of the Investigator's responsibility for ensuring that all clinical data entered on the CRF are complete, accurate, and authentic. The CRF data is entered into a validated database.

8 ETHICAL, LEGAL AND QUALITY ADMINISTRATIVE ASPECTS

8.1 Good Clinical Practice

The procedures set out in this study protocol are designed to ensure that the individual treatments as well as the investigator abide by the principles of the Good Clinical Practice (GCP) guidelines of the ICH. The study will be carried out to abide with local legal and regulatory requirements.

Both Sponsor and Principal Investigator confirm this by signing this study protocol (see Page 2-3).

8.2 Changes in Statistical Methods

All changes in statistical methods that are described in the statistical analysis plan (SAP) will be documented in the clinical study report.

8.3 Informed Consent

Before being admitted to the study, informed consent will be obtained from each patient (or his/her legally authorized representative) according to the regulatory and legal requirements of the United States. This consent form must be dated and retained by the investigator as part of the study records.

Should a protocol addendum be made, the patient consent form may be revised to reflect the changes of the protocol.

If the consent form is revised, it is the responsibility of the investigator to ensure that an amended consent is reviewed and approved by the IRB. The approved amended consent form should be signed by all subjects subsequently entered in the study and those currently in the study.

The investigator will not undertake any investigation specifically required only for the clinical study until valid consent has been obtained. The terms of the consent and when it was obtained must also be documented in the CRF.

8.4 Approval of Study Protocol

Upon finalization of the original study Protocol, the Investigator Signature Page and Sponsor Signature Page are to be executed by each party representative as an acceptance and agreement of the Protocol.

Before the start of the study, the study protocol and/or other appropriate documents will be submitted to the IRB in accordance with local legal requirements.

The sponsor and the investigator must inform each other in writing that all ethical and legal requirements have been met before the first patient is enrolled in the study.

8.5 Confidentiality

All study findings and documents will be regarded as confidential.

The anonymity of participating subjects must be maintained. Subjects will be identified on CRFs and other documents by their initials, birth date, and patient number.

8.6 Ethics Committee and Regulatory Authorities

Before enrollment of subjects into this study, the protocol, ICF and any promotional material or advertisements will be reviewed and approved by the appropriate IRB and regulatory authorities, where applicable. The study will commence only when the committee has approved the protocol or a modification thereof and a copy of the approval letter is received.

It is the investigator's responsibility to obtain IRB approval for the protocol and all subsequent major changes, in compliance with local law.

8.7 Monitoring

The study monitor and/or other authorized representatives of the Sponsor is/are responsible for monitoring that each study site conducts the study according to the protocol, SOPs, other written instructions, Code of Federal Regulation (Title 21, CFR Part 812) and applicable regulatory guidelines. The investigator will permit the study monitor or other authorized representatives to visit the study site at appropriate intervals to observe the progress of the study, review study records/documentation, and ensure that informed consent has been obtained for each subject prior to performing any study procedure.

8.8 Auditing

The Sponsor and/or Sponsor's representatives may conduct audits (quality assurance) to evaluate study conduct and compliance with the protocol, SOPs, other written instructions/agreements, Code of Federal Regulation (Title 21, CFR Part 812) and applicable regulatory guidelines/requirements. The investigator will permit auditors to visit the study site. The quality assurance auditor will have access to all medical records, the investigator's trial-related files and correspondence, and information in the informed consent documentation of this clinical trial.

9.0 Research Study Assessments

Primary Endpoint Evaluations

Hand Eczema Severity Index:

Clinical Signs	Fingertips	Fingers (except tips)	Palms of Hands	Backs of Hands	Wrists
Erythema (E)					
Infiltration (I)					
Vesicles (V)					
Fissures (F)					
Scaling (S)					
Oedema (O)					
SUM					
Extent					
Total HECSI Score = _____	SUM * Extent	SUM * Extent	SUM * Extent	SUM * Extent	SUM * Extent

Reference: Held et al – British Journal of Dermatology – Volume 152 Issue 2 (2005) pages 302-307

Each hand is divided into five areas [fingertips, fingers (except the tips), palms, back of hands and wrists]. The clinical signs of erythema, induration/papulation, vesicles, fissuring, scaling and oedema are graded on the following scale:

0 = no skin changes

1 = mild disease

2 = moderate

3 = severe

Per each location (combining both hands), the affected region was given a score for extent of surface area involvement on the following scale:

0 = 0%;

1 = 1–25%

2 = 26–50%

3 = 51–75%

4 = 76–100%

Finally, the score given for the extent at each location was multiplied by the sum of the intensity of clinical features. The total sum (HECSI score, highlighted above) was calculated, ranging from 0 to a maximum severity score of 360.

Investigator's Global Assessment:

The investigator will rate the subject's hand dermatitis on a visual 5-point scale as follows:

0: Clear:	No signs of HE
1: Almost clear:	Just perceptible scaling and/or erythema;
2: Mild disease:	Mild scaling and/or mild erythema, and/or mild cracking
3: Moderate disease:	Moderate scaling and/or erythema, and/or moderate cracking/fissuring
4: Severe disease:	Severe scaling and/or severe erythema, and/or severe cracking/fissuring

Dorsal and palmar surfaces of the hand are evaluated *together*.

Reference: Diamant et al. - Dermatology Basel - Volume 207, Issue 1 (2003) pages 37-42

Secondary Endpoint Evaluations

Subject's Local Dermal Tolerability Assessment:

The subjects will be asked to grade their feeling of itching at the application site using a 4-point tolerability scale, where 0=None, 1=Mild, 2=Moderate, and 3=Severe.

Puritus: Definition: itching

0 = None:	No itching
1 = Mild:	Occasional, slight itching/scratching
2 = Moderate:	Constant or intermittent itching/scratching/discomfort that is not disturbing sleep
3 = Severe:	Bothersome itching/scratching/discomfort that is disturbing sleep

Local Skin Reaction Assessment:

The investigator or designee will describe his/her assessment of the subject's hands at the moment using a 4-point tolerability scale, where 0=None, 1=Mild, 2=Moderate, and 3=Severe.

Erythema: Definition: abnormal redness of the skin

0 = None:	No erythema
1 = Mild:	Slight pinkness present
2 = Moderate:	Definite, dull redness that is clearly distinguishable
3 = Severe:	Intense, deep redness

Induration/Papulation: Definition: inflammation, swelling

0 = None:	No elevation
1 = Mild:	Slightly perceptible elevation
2 = Moderate:	Clearly perceptible elevation but not extensive
3 = Severe:	Marked and extensive elevation

Lichenification: Definition: thickening upper layers of skin

0 = None: No thickening

1 = Mild: Slight thickening of the skin discernible only by touch and with skin markings minimally exaggerated

2 = Moderate: Definite thickening of the skin with skin markings exaggerated so that they form a visible crisscross pattern

3 = Severe: Thickened, indurated skin with skin markings visibly portraying an exaggerated crisscross pattern

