Safety Endpoints:	
Safety/tolerability endpoints are monitored by members of the study staff. They include the following:
 
 - Changes in local skin reaction - Changes in AEs and serious adverse events (SAEs) - Changes in vital signs and physical examinations - Changes in concomitant procedures/medications - Presence of signs/symptoms of irritation of the skin.
Statistical Methods:	
 - All analyses of the pooled individual patient data will be performed with the use of SPSS software using a two-way Chi-square test analysis, t-tests, odds ratios, and analysis of variance (ANOVA).
Assessments:	
 - Hand Eczema Severity Index 
 o Investigator-rated: clinical evaluation of both the extent and intensity of hand dermatitis 
 ▪ Clinical signs: erythema, infiltration/papulation, vesicles, figures, scaling, and edema ▪ Locations: fingertips, fingers (excluding tips), palms of hands, backs of hands, wrists ▪ Extent is graded on a visual 5-point scale ▪ Intensity is graded on a visual 4-point scale - Local Skin Reaction Assessment 
 o Investigator-rated: clinical grading score of erythema, induration/papulation, and lichenification 
 ▪ Each parameter is graded on a visual 4-point scale - Subject's Local Dermal Tolerability Assessment: 
 o Subject-Rated: clinical grading score of pruritus 
 ▪ Each parameter is graded on a visual 4-point scale - See assessments reference at end
Randomization:	
 - The subjects will be randomized to receive either the active or control medication based on a 3:1 randomization scheme - Out of 20 total subjects, 15 will receive the active treatment while 5 will receive the vehicle
Photography:	
 - Digital photographs will be taken at proximal and distal views of the dorsal as well as palmar surfaces of the hand

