4 STUDY POPULATION

4.1 Inclusion Criteria

Subjects who meet all of the following criteria are eligible for this study:

1. Subject is a male or non-pregnant female, 12 years of age and older.
2. Subject is willing and able to provide written informed consent for the study.
3. Subject is willing and able to apply the investigational product as directed, comply with study instructions and commit to all follow-up visits for the duration of the study.
4. Subject has clinical diagnosis of mild to moderate hand dermatitis for at least 3 months.
5. Subject has a baseline Investigator's Global Assessment (IGA) score of 2 or 3 (disease severity of mild or moderate).
6. Subject is in good general health and free of any disease state or physical condition that might impair evaluation of hand dermatitis or which, in the investigator's opinion, exposes the subject to an unacceptable risk by study participation.
7. Women of childbearing potential (WOCBP) must use an effective method of birth control or must be post-menopausal or surgically sterile. Women of childbearing potential (WOCBP) must have a negative urine pregnancy test (UPT) at Baseline.

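### By-arm summaries of the two primary tolerability scales can offset improvement of the dermatitis in some subjects against irritation in others; a count of subjects worse than their own baseline should be added

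*Combined protocol and SAP*

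**What the plan says.** Section 7.2.8.2 states that the Local Skin Reaction Assessment and the Subject's Local Dermal Tolerability Assessment "will be the primary modes of tolerability evaluation". Section 3.1 places both under the secondary objective.

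- **Subject scale** (section 9.0): "The subjects will be asked to grade their feeling of itching at the application site", scored 0 to 3. The wording of grades 2 and 3 also mentions discomfort, but itch is the only item.
- **Investigator scale** (synopsis, Assessments): a "clinical grading score of erythema, induration/papulation, and lichenification", each item scored 0 to 3. Section 9.0 tells the rater what to look at: "The investigator or designee will describe his/her assessment of the subject's hands at the moment using a 4-point tolerability scale". It gives no rule for telling a reaction to the product from the dermatitis.
- **Efficacy scale** (section 9.0, HECSI): "The clinical signs of erythema, induration/papulation, vesicles, fissuring, scaling and oedema are graded on the following scale".

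The hand is both the diseased site and the treatment area (6.4.2). Both tolerability scales are read at Visits 2, 3 and 4 (6.3), and the skin-reaction baseline is taken before the first application (6.4.2). The synopsis lists change in local skin reaction as an endpoint.

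Section 7.2.1 provides listings of all data, descriptive statistics by arm for continuous data and frequency tables by arm for categorical data. It does not say whether the tables show grades or changes in grade. No within-subject shift or worsening count is specified.

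**The concern.** When a product works, erythema on the treated hand falls. When a product irritates, erythema on the same hand rises. The investigator scale records both on one item, with opposite signs, and the same is true of induration/papulation. A mean over the arm, or a table of how many subjects hold each grade, gives only the net result.

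The vehicle arm does not remove this. If the active product is effective, it improves these items more than vehicle does, and that extra improvement is what can cover the irritation.

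At stake is how the secondary objective is read. Section 7.2.8.2 rules out statistical testing of safety data, so the descriptive summary is the main evidence from these scales and its form matters.

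**Working it through.** The plan gives no figure for tolerability that could be reproduced. The check is a comparison of items, followed by arithmetic on assumed rates. Only the arm sizes (15 active, 5 vehicle, section 7.2.2) and the 0 to 3 scales come from the documents.

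**1. Item overlap (section 9.0)**

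| Tolerability item | In HECSI? | In IGA wording? |
|---|---|---|
| Erythema ("Erythema: Definition: abnormal redness of the skin") | yes | yes |
| Induration/papulation | yes | no |
| Lichenification | no | no |
| Itch | no | no |

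So 2 of 4 items are also efficacy signs. The other 2 are graded on the same skin but are in neither efficacy scale.

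**2. Offsetting between subjects, means**

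Assume that 20% of active subjects end one grade worse, that half of the rest improve by one grade, and that 20% of vehicle subjects improve and none worsen.

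- Active: 0.20 × (+1) + 0.80 × 0.50 × (-1) = 0.20 - 0.40 = -0.20. In subjects: 3 worse, 6 better, 6 unchanged.
- Vehicle: 0.20 × (-1) = -0.20. In subjects: 0 worse, 1 better, 4 unchanged.

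The means are equal, with 3/15 against 0/5 worse.

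**3. Range**

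Let e be the extra improvement on active over vehicle, in points, and s the share of active subjects with one point of irritation. Ignoring the limits of the scale, the net active-minus-vehicle change is s × 1 - e, and a negative value favours active.

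| e | s = 20% | s = 33% | s = 50% |
|---|---|---|---|
| 0 | +0.20 | +0.33 | +0.50 |
| 0.25 | -0.05 | +0.08 | +0.25 |
| 0.5 | -0.30 | -0.17 | 0.00 |

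Masking therefore depends on efficacy. With no extra improvement, the irritation shows.

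**4. Grade frequencies**

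Assume that 5 active subjects start at grade 1 and 10 at grade 2. Three go from 1 to 2 and six go from 2 to 1. Grade 2 then holds 10 - 6 + 3 = 7 and grade 1 holds 5 - 3 + 6 = 8. The table reads as improvement, and the three worsenings cannot be seen. Had all subjects started at one grade, they could be.

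**5. What a worsening count can and cannot show**

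- Within a subject, one point better and one point irritated gives b - 1 + 1 = b for a baseline b of 1, 2 or 3. The change is 0 and the count misses it.
- A subject at baseline grade 3 cannot worsen on the scale.
- Exact 95% intervals: 3/15 gives about 4% to 48%, and 0/5 gives 0% to 52%.

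**6. Adverse events as a second source**

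If every case is reported, the chance of at least one irritation event among 15 active subjects is 1 - (1 - p)^15: 54% at p = 5%, 79% at 10% and 96% at 20%.

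**The case against.** The strongest reply is that the trial has other ways to see irritation.

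- Section 7.2.1 lists all data, so with 20 subjects each grade at each visit can be read.
- It also asks for the standard deviation, minimum and maximum. If these are applied to change scores, the illustration in step 2 shows a maximum change of +1 on active against 0 on vehicle. A frequency table of change would show 3/15 against 0/5 directly.
- Section 6.1.1.2 has subjects questioned from a checklist of skin reactions and has events graded for relationship to treatment. Section 7.2.8.2 tabulates events by arm, severity and relationship.
- The synopsis lists signs or symptoms of irritation as an endpoint, though with no scale or analysis.

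All of this stands, and it limits the point to the planned group summaries. It does not remove the point: listings are not a summary, the plan does not commit to tabulating change in grade, and the named primary measures remain mixed.

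A reader might infer three stronger things that the documents do not support:

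- **That all four items are the disease itself.** The overlap is documented for two. That itch and lichenification also reflect the dermatitis is a reasonable reading, no more.
- **That every subject starts above zero on each item.** Entry requires this: "Subject has a baseline Investigator's Global Assessment (IGA) score of 2 or 3 (disease severity of mild or moderate". But grade 2 reads "Mild scaling and/or mild erythema, and/or mild cracking", so scaling alone can qualify, and the IGA wording does not mention papulation, lichenification or itch. No baseline distribution is given.
- **That local tolerability cannot be assessed apart from efficacy.** The adverse-event route above is separate from the two scales.

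**Conclusion.** The point holds for the by-arm means and grade frequencies of the two scales. On these summaries an effective but irritating product could look as well tolerated as vehicle, or better. The documents do not show that it would.

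The size rests on assumed rates. Mean change is equal at -0.20 with 3/15 against 0/5 worse, and the net difference is -0.30 to 0.00 when active improves the item by 0.5 points more than vehicle and 20% to 50% of active subjects are irritated by one point. With smaller extra improvement, the masking shrinks or disappears.

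This is a weakness in how tolerability is summarised, not a failure to collect the data, and it is cheap to put right. The remedy is partial, and with 15 and 5 subjects the resulting proportions will be imprecise.

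**What to change.** In 7.2.8.2, add for each of the four items the number and percentage of subjects per arm with any post-baseline grade above their own Visit 2 grade, with exact 95% confidence intervals. Present it as a shift table by baseline grade, so that subjects at grade 3, who cannot worsen, are visible. Read it beside the skin-reaction adverse events by relationship to treatment.

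State the limits in the same place. The count removes offsetting between subjects only. It misses offsetting within a subject and any worsening from baseline grade 3. It includes ordinary flares of the dermatitis, and it is imprecise at these arm sizes.

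The cost is a few sentences and a table from data already collected at Visits 2, 3 and 4.

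Optionally, add one 0 to 3 line for burning or stinging to the subject form. Neither HECSI nor the IGA scores it, so improvement on the efficacy scales does not feed into it by construction. The adverse-event checklist is not reproduced in the protocol and may already ask about it, so check that first. The cost is one form line at three visits.
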